After the first day of desensitization, subjects will return to the research unit to begin the build-up phase of the study. The subject will ingest 6 mg, or a lower amount based on the reaction to the modified rush phase. After the subject is observed for a minimum of 30 minutes for symptoms to the study protein ingestion, he or she will be discharged from the research unit and will continue to consume the study protein at home daily for a minimum of ten to fourteen days (+7 days). The family receives the study protein doses as a powder that they give to the child each day by sprinkling it on a previously tolerated food (e.g., applesauce). Subsequently, subjects will return to the clinical research unit every ten to fourteen days to monitor their adherence to the dosage administration and increase the dose to the next escalation amount (see Table 4). The subject's response to the new dose escalation amount will be monitored for a minimum of 30 minutes after dose administration. Vital signs are performed prior to the dose administration, prior to the completion of the observation period before discharge, and anytime symptoms occur. If attempts at blood pressure measurement have been very disturbing and traumatic to a young child, the study team will rely on observation, heart rate and respiratory rate and the physical assessment to determine the subject's response. If the study team feels that a longer observation time is warranted based on the prior dosing history of the subject or their current physical status, the subject will be observed for a longer period of time. If symptoms occur that do not require treatment, the subject will be observed until they resolve. If symptoms occur that require diphenhydramine or albuterol, the subject will be observed a minimum of 2 hours or until symptoms resolve. If symptoms occur that require epinephrine, the subject will be observed at least 4 hours or until symptoms resolve. If symptoms do not fully resolve after 6 hours or if new symptoms occur, the subject will be transferred to UNC Children's Hospital to be observed overnight. Subjects will then take that dose daily for a period of 10 to 14 days (+ 7 days) after which they will return to the clinical research unit to have the daily dose increased proportionately at each visit until the maximum daily dose of study protein (3000mg) is consumed. All active subjects will build up to 3000mg of study protein. To maintain blinding, the subjects randomized to the 300mg peanut dose will have additional placebo flour added to the study protein during buildup by unblinded study personnel. Laboratory studies will be done at the beginning of the study, when the subject reaches the 156 milligram dose, when the subject reaches the 749 milligram dose, and when the subject reaches the 3000mg dose, and annually thereafter until the end of the study. The laboratory studies will consist of blood tests to monitor the immune response to the peanut protein. Stool studies will be performed at the beginning of the study and the end of the study. Control subjects will have visits for medical history, physical exam, titrated skin prick testing and blood and stool laboratory studies associated with the study at entry and then yearly. This control group will be seen yearly over the length of the study.

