After completing the escalation schedule (*build up phase* to 3000 mg study protein), the subjects will continue to receive their maintenance dose of study protein daily for the next 36 months of the study (*maintenance phase*). Once subjects enter the maintenance phase, assessment of the primary endpoint will occur conditionally (i.e., upon achievement of defined immunological benchmarks), and/or at the chronological end of 36 months of maintenance. These two possible scenarios are discussed further below. After 12 months of maintenance, the subject will have the peanut-specific IgE measured. In the first conditional scenario, at any point after this measurement, if the peanut IgE is 15 kU/L or less, the skin test is 8mm or less, and there have been no severe symptoms following PMIT doses or accidental peanut exposure in the previous 6 months, at the discretion of the investigator, the subject will stop the daily dosing and have a DBPCFC the next day. This cohort of subjects will then stop the daily dosing for the next 4 weeks and then return for a 2nd DBPCFC to peanut to assess long term tolerance to peanut. If these food challenges are negative (i.e., successfully completed), they will be followed by an open peanut challenge. The open challenge will occur in a 1 to 2 hour window after the successful completion of the tolerance challenge, and the study will be completed for that participant if the open challenge is successful. If any of the challenges are positive or inconclusive (i.e., not successful), the participant will resume OIT dosing until the next 12 months, or at the end of the 36 month treatment period. In the second (i.e. chronological) scenario, all remaining subjects will be assessed for the primary endpoint once they have completed 36 months of maintenance treatment, regardless of their immunologic parameters and/or their performance in past challenges, if applicable. If either challenge at the end of 36 months are positive or inconclusive (i.e., not successful), the participant will be considered as having completed the study and will return to standard of care.

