Subjects will come to the UNC Food Allergy Study Center (FASC) for a double-blind, placebo-controlled food challenge (DBPCFC) at the end of the 36 month maintenance treatment period, or sooner if challenge criteria are met. The DBPCFC may either occur on 1 day or over a 2 day period. The food challenges will be administered by the study coordinators or research nurses associated with the study. In a double-blind, placebo controlled challenge, two challenges, one containing placebo (which will be oat flour) and one containing peanut, will be performed in the same day. Randomization and preparation of the challenge materials will be performed by the dietitian or a representative from [name] laboratory. Prior to the food challenge, subjects will be asked to restrict the use of antihistamines (short acting, 72 hours; long acting, 7 days), beta-agonists (12 hours), theophylline (12 hours), and cromolyn (12 hours). One challenge will consist of six doses of peanut given every 10-20 minutes in increasing amounts up to a total weight of 5 grams of peanut protein. The other challenge will consist of placebo material given also in six doses. The cumulative dose of peanut protein given is 5 grams (10 gram weight of peanut flour). Both challenges will start by first touching the patient's lip/tongue with a small amount of the test material. The first ingested dose will be 0.5 grams (5%), then increasing to 1 gram (10%), 2 grams (20%), 2.0 grams (20%), 2 grams (20%), and 2.5 grams (25%). During food challenges, vital signs will be performed prior to the challenge, between the two parts of the challenge, at the end of the challenge day, and anytime symptoms occur. Prior to each challenge, the patient will have a medical history and physical exam performed, during which emphasis will be placed on active respiratory symptoms such as wheeze and cough. The challenge will be administered by a nurse or physician who is blinded to the testing material. The supervising investigator will also be blinded to testing material.

If the subject ingests all of the challenge material without significant symptoms, the treatment will be stopped for 4 weeks, and the DBPCFC will be repeated, using the same procedure as described above. At the end of these challenges, **all negative challenge results will be confirmed by open challenge to peanut. Approximately 5 grams of peanut protein will be the quantity of peanut given in the open challenge.**

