After each challenge the patient will be observed for a minimum period of 1 hour. Reactions will be scored using a Food Challenge Symptom Score sheet (page 24 and 25 of the protocol). If the patient begins to have any objective symptoms or subjective symptoms deemed clinically significant, the food challenge will be terminated and the patient will be given appropriate treatment. Symptoms which would result in discontinuation of the ongoing part of the DBPCFC include diffuse hives, throat/tongue swelling, wheezing, respiratory distress, emesis, moderate to severe abdominal pain and hypotension. These would be treated with the appropriate emergency medication and the subject would enter a minimum 2 hour observation period or until symptoms resolve. If no symptoms are reported during the first part of the DBPCFC, the subject would enter the observation period. If the subject is stable after the observation period, the second part of the DBPCFC would then commence. If epinephrine is required to treat symptoms, the subject would be observed for a minimum of 4 hours and the second part of the challenge will be deferred until the next day. The subjects who are not symptomatic will be observed for a minimum of 2 hours after the challenges are completed before being discharged from the FASC. All food challenges will be performed under physician supervision.

If the subject fails the tolerance challenge after being off the study protein for 1 month, the subject will be discharged home to continuing daily dosing on the highest tolerated dose of the challenge. The subject will continue this dose and have the desensitization and tolerance challenges repeated in one year or at the chronological end of their 36 month maintenance period, whichever comes first.

Individual Stopping Rules

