DUKE IRB# 00016160
 UNC IRB# 11-2307
 Principal Investigator: [name]
 Co-Investigator: [name]

DEVIL

Dosage Escalation Sheet

(*Record time in 24 hour clock)

Subject Number _____
 Date of visit ____/____/____
 Date of Desensitization ____/____/____
 Randomization #: _____
 Current Daily Dose _____
 Dose to be given today _____

Food used for dosage escalation _____; Use 1 Tablespoons per dose of peanut.

Clock time*	Running time (Minutes)	Amount Food Challenge	SKIN				UPPER RESPIRATORY				CHEST	ABDOMEN		
			% Area Rash IA	IB	Pur. IC	Urt/Ang. ID	Sneez/ Itch IIA	Nasal/ Cong IIB	Rhin IIC	Laryn. IID	Wheeze IIIA	Subj Comp IVA	Obj Comp IVB	
:														
:														
:														
:														
:														
:														
:														
:														
:														
:														
:														
:														
:														
:														

Comments: _____

Symptom Scoring Sheet for Desensitization, Dosage Escalations, and Oral Food Challenges

I. Skin

A. Erythematous rash - _____% area involved

B. Rash

0 Absent

1 Mild – few areas of faint erythema

2 Moderate – areas of erythema, macular and raised rash

3 Severe – generalized erythema (>50%), extensive raised lesions (>25%)

C. Pruritus

0 Absent

1 Mild – occasional scratching

2 Moderate – scratching continuous for more than 2 minutes at a time

3 Severe – generalized involvement

D. Urticaria/Angioedema

0 Absent

1 Mild – less than 3 hives

2 Moderate – greater than 3 but less than 10 hives

3 Severe – generalized involvement

II. Upper Respiratory

A. Sneezing/Itching

0 Absent

1 Mild – rare bursts

2 Moderate – less than 10 bursts, intermittent rubbing of nose and/or eyes

3 Severe – continuous rubbing of nose and/or eyes, periocular swelling and/or long bursts of sneezing

B. Nasal Congestion

0 Absent

1 Mild – some hindrance to nasal breathing

2 Moderate – nostrils feel blocked; breathes through mouth most of the time

3 Severe – nose runs freely despite sniffing and tissues

C. Rhinorrhea

- 0 Absent
- 1 Mild – occasional sniffing
- 2 Moderate – frequent sniffing, requires tissues
- 3 Severe – nose runs freely despite sniffing and tissues

D. Laryngeal

- 0 Absent
- 1 Mild – throat clearing, cough
- 2 Moderate – hoarseness, frequent dry cough
- 3 Severe – inspiratory stridor

III. Chest

A. Wheezing

- 0 Absent
- 1 Mild – expiratory wheezing to auscultation
- 2 Moderate inspiratory and expiratory wheezing
- 3 Severe – dyspnea, use of accessory muscles, audible wheezing

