**Determining the Efficacy and Value of Immunotherapy on the
likelihood of peanut tolerance: The DEVIL Study**

Statistical Analysis Plan

NCT number NCT00932828

Document Date 04/08/2013

Sample size

No placebo-controlled studies have been published that evaluated the development of tolerance/SU after years of treatment with peanut OIT. Published data from our own uncontrolled pilot study in older children with long-standing disease suggest that SU developed in 12 of 24 (50%) peanut-allergic subjects completing high-dose OIT. (Vickery, et al. Sustained unresponsiveness to peanut in subjects who have completed peanut oral immunotherapy. *J Allergy Clin Immunol*. 2014 Feb;133(2):468-75. doi: 10.1016/j.jaci.2013.11.007). On the basis of preliminary data that were available to us at the time this study was conceived in 2008, and according to our hypothesis, we predicted before the study that 70% of low-dose subjects would develop SU, compared with the expected rate of spontaneous peanut allergy resolution of 20% as shown in multiple cohort studies. At a 2-sided significance level of .05, 15 subjects in each treatment arm would have at least 80% power to detect a 50% absolute average difference between the proportion of subjects in each arm passing the exit SU OFC and the 20% rate of spontaneous tolerance expected in untreated controls. On the basis of a prestudy assumption of 15% to 20% dropout, we enrolled 20 subjects per arm to ensure adequate power.

Practical considerations prevented a trial large enough to show definitive comparisons of high- and low-dose therapy directly. Twenty subjects in each arm would have 63% power to identify a 40% difference in SU acquisition between regimens. Even if underpowered to show a difference between low-dose and high-dose therapy, we reasoned a priori that a type II error in this setting may still be clinically meaningful so long as the proportion achieving SU in the low-dose group significantly exceeded 20%. This would be especially true if low-dose therapy offers other advantages (fewer visits, better safety profile, improved palatability, etc).

Randomization

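### The restart dose after a failed early tolerance challenge is not tied to the randomised dose, so a low-dose child may be re-challenged, and counted, after months above 300 mg

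*Protocol*

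**What the plan says.** **Who is affected.** After 12 months of maintenance, a child who meets the IgE, skin-test and symptom criteria may be challenged early at the investigator's discretion (Protocol, Study Design, Dosage Schedule, and Accidental Reactions). A child who passes stops dosing for 4 weeks and is challenged again for tolerance.

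**Restart.** For a failure at that second challenge, the food-challenge paragraphs just before Individual Stopping Rules say that "the subject will be discharged home to continuing daily dosing on the highest tolerated dose of the challenge". They continue: "The subject will continue this dose and have the desensitization and tolerance challenges repeated in one year", or at month 36 if that is sooner. The maintenance-phase paragraph covers the same event but gives no dose: "the participant will resume OIT dosing until the next 12 months, or at the end of the 36 month treatment period". A failure at month 36 ends participation, so the restart rule applies only to earlier failures.

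**Masking.** The build-up paragraph says that "the subjects randomized to the 300mg peanut dose will have additional placebo flour added to the study protein during buildup by unblinded study personnel". The SAP (Randomization) describes the oat-flour masking of the low-dose product without limiting it to a phase.

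**Analysis.** The SAP (Sample size) bases its power on "the proportion of subjects in each arm passing the exit SU OFC", compared with a 20% spontaneous rate. It argues that a failure to separate the two doses may still be informative "so long as the proportion achieving SU in the low-dose group significantly exceeded 20" percent. Under Randomization, it pools the arms for the primary outcome and makes the dose comparison exploratory. Neither document says how a restarted child is handled in the count by arm.

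**The concern.** The challenge doses were chosen to test reactivity, not to match the treatment arms. No challenge step, and no running total, equals 300 mg or 3000 mg of peanut protein. If the restart is literally a challenge dose of peanut, a child randomised to 300 mg can spend the months before the deciding challenge on considerably more. A pass would then support a statement about 300 mg that the child's recent dosing does not match.

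The exploratory comparison of the two doses is exposed as well. If the restart is a single challenge step, restarted children in both arms fall in the same range, and the tenfold contrast is lost for them. The protocol calls the study dose-finding and hypothesises that low dose does as well as high dose, so the plan should be clear about what dose these children took.

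**Working it through.** **Inputs** (Protocol, food-challenge paragraphs): six steps of 0.5, 1, 2, 2, 2 and 2.5 g of flour; 10 g flour carries 5 g protein. Randomised doses are 300 and 3000 mg peanut protein (SAP, Randomization).

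**The plan's own total.** 0.5 + 1 + 2 + 2 + 2 + 2.5 = 10 g flour, and 10 × 0.5 = 5 g protein. This agrees with the protocol.

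**Restart dose.** Protein (mg) = flour (g) × 1000 × 0.5. Tolerating all six steps is a pass, so the last step tolerated by a failing child is at most step 5. The protocol does not say whether the dose means the single step or the running total, so both are shown. The last column is min(single step, 300); on the cumulative reading it is the same.

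| Last step tolerated | Flour (g) | Single step (mg protein) | Cumulative (mg protein) | Low-dose restart if capped (mg peanut protein) |
|---|---|---|---|---|
| 1 | 0.5 | 250 | 250 | 250 |
| 2 | 1 | 500 | 750 | 300 |
| 3 | 2 | 1000 | 1750 | 300 |
| 4 | 2 | 1000 | 2750 | 300 |
| 5 | 2 | 1000 | 3750 | 300 |

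A child who reacts at step 1 has tolerated no ingested step, and the rule then gives no restart dose.

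- Low-dose arm: from step 2 on, the uncapped restart exceeds 300 mg on both readings. Single step: 500/300 = 1.7 times to 1000/300 = 3.3 times. Cumulative: up to 3750/300 = 12.5 times.
- High-dose arm: all five single-step values are below 3000 mg. On the cumulative reading four are below and one (3750 mg) is above.

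**Duration.** The earliest early challenge is at about month 12 of maintenance, and the tolerance challenge follows 4 weeks later, at about month 13. Re-challenge comes one year on, at about month 25, or at month 36 if sooner. The restart dose is therefore taken for up to about 12 months before a re-challenge.

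**How far the low-dose conclusion depends on this.** The SAP names no test for the low-dose arm against 20%; an exact two-sided binomial test is assumed here. The SAP's 20 per arm is used (the protocol gives 40).

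- Planned result: 0.70 × 20 = 14 of 20.
- Against 0.20 with n = 20: 7 passes give p = 0.098 and 8 give p = 0.044, so 8 is the lowest significant count.
- The planned 14 is 14 − 8 = 6 passes above that threshold.

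The SAP's statement that 15 per arm give at least 80% power for 70% against 20% reproduces at 82.0% (pooled normal approximation). It is not in question.

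**The case against.** The strongest reply is that the restart is meant to be masked study protein, as in build-up. The SAP describes masking of the low-dose product in general terms, families and investigators are blinded, and the maintenance-phase paragraph speaks of going back to immunotherapy dosing. On that reading, a low-dose child at a 500 or 1000 mg step would receive at most 300 mg peanut, and the low-dose problem disappears. This is plausible. It is not settled, because the protocol places the flour addition in build-up and a dose of the challenge is, on its face, an amount of peanut.

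The rule also has a sound safety purpose: the child has just reacted after 4 weeks off treatment, so dosing resumes at an amount known to be tolerated. That stands. On the single-step reading, a restart below 3000 mg in the high-dose arm is unavoidable.

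The reach is narrow. A child must qualify early, pass one challenge, fail the next before month 36, and pass later. The documents do not say how many would.

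Three stronger readings are tempting and are not supported:

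- *The low-dose SU rate is inflated.* An affected child has also had build-up and at least 12 months of assigned 300 mg maintenance. Neither the size nor the direction of any effect is established.
- *The low-dose conclusion hangs on a pass or two.* At 8 of 20, the lowest significant count, losing one pass reverses significance by construction. That says nothing about this rule.
- *Analysis by randomised arm is wrong.* It is right; what is missing is a display of the dose actually taken.

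**Conclusion.** The concern holds as a gap in the restart rule. Read literally, the protocol lets a low-dose child who tolerated step 2 or beyond take 500 to 1000 mg peanut protein, or 750 to 3750 mg on the cumulative reading, for up to about 12 months before a re-challenge whose result counts as low-dose SU. This depends on the restart not being dispensed as masked study protein capped at 300 mg peanut, which the documents leave open.

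The consequences are limited. The pooled primary comparison with controls is unaffected. At the planned 70% SU rate the low-dose conclusion is robust, under the assumed binomial test. The dose comparison that could be blurred is exploratory and acknowledged to be underpowered. This is a cheap improvement, not a threat to the trial's main result.

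**What to change.** **Protocol.** In both the maintenance-phase paragraph and the food-challenge paragraph, state that the restart after a failure before month 36 is dispensed by unblinded staff as masked study protein. Its peanut content should be the lower of the highest tolerated challenge dose and the randomised dose, so a low-dose child never receives more than 300 mg peanut. Say whether the tolerated dose means the single step or the running total. Leave the return towards 3000 mg study protein to the investigator, where tolerated.

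**Data.** Record the actual peanut dose taken before each re-challenge. The Dosage Escalation Sheet already has a "Current Daily Dose" line, but the peanut content must come from the unblinded dispensing record.

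**SAP.** Keep the analysis by randomised arm. Report descriptively, by arm, the number of SU passes reached after an off-dose restart. Do not add a sensitivity analysis that scores those passes as failures. With the cap in place, the only off-dose restart left in the low-dose arm is 250 mg, so that analysis would mainly turn high-dose passes achieved on less peanut into failures, which has no rationale.

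**Cost.** One extra data field, a table row or two, and no added visits. Some low-dose children restart on a lower dose than the literal rule allows; the cap never raises a dose.
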